3.2 Study Endpoints

3.2.1 Primary Endpoint

GOS evaluated at Month 6 post-injury.

3.2.2 Secondary Endpoints

Secondary endpoints will be assessed by the following measures:

- Mortality assessment at 1 month and 6 months post TBI
- Evaluation of GOS at 3 months

- Evaluation of the GOS-E at Months 3 and 6
- SF-36 at Months 3 and 6
- Changes in ICP, CPP, and TIL
- Changes in intracranial pathology as assessed by the admission and end-infusion Day 6 (+/-1 Day) CT scans.

4. SELECTION OF STUDY POPULATION

One thousand one hundred and eighty subjects (1180) will be enrolled in this trial. Patients who have severe TBI and who meet the following inclusion/exclusion criteria will be eligible.

4.1 Inclusion Criteria

1. Male or female patients, age between 16 and 70 years, inclusive (or other age limit as required by local regulations)
2. Weight from 45 to 135 kg, inclusive
3. Sustained a closed head trauma no more than 8 hours before initiation of study drug infusion (exposed dura mater is acceptable in the case of depressed skull fractures)
4. TBI diagnosed by history and clinical examination
5. GCS score between 3 and 8, inclusive
6. At least one reactive pupil (pinpoint pupils due to opioid pain treatment are considered reactive)
7. Evidence of TBI confirmed by abnormalities consistent with trauma on CT scan upon admission (diffuse injury II-IV, evacuated and non-evacuated mass lesion, Marshall's CT Classification)
8. Indication for ICP monitoring

4.2 Exclusion Criteria

1. Life expectancy of less than 24 hours as determined by the Investigator
2. Prolonged and/or uncorrectable hypoxia ($\text{PaO}_2 < 60 \text{ mmHg}$) or hypotension (systolic blood pressure $< 90 \text{ mmHg}$) at the time of randomization
3. Any spinal cord injury
4. Pregnancy
5. Patients with penetrating head injury
6. Bilaterally fixed dilated pupils at the time of randomization
7. Coma suspected to be primarily due to other causes (e.g. alcohol)
8. Pure epidural hematoma
9. Preexisting clinically significant disease or chronic condition that can be ascertained at the time of admission and could affect functional outcome
10. Severe cardiac or hemodynamic instability prior to randomization
11. Known treatment with another investigational drug, device, medical therapy or procedure within 30 days of injury
12. A history of allergic reaction to progesterone and related drugs or any of the components of the infusion
13. Any disease, in the opinion of the Investigator, that is unstable or which could jeopardize the safety of the patient and his/her compliance in the study.
14. Patients who, in the opinion of the Investigator, would not be able or willing to comply with the protocol through the final visit (6 months post-injury)

4.3 Withdrawal of Subjects from the Study

A good faith effort will be made to ensure that subjects complete the study through the 6-month assessments, consistent with the provisions of informed consent and good clinical judgment with respect to safety. The following are potential reasons to terminate the participation of a subject in the study:

- The subject's health would be jeopardized by continued participation.
- Lost to follow-up: subject fails to return to the study site for scheduled visits and does not respond to multiple telephone or written attempts to contact. (Note: if subject cannot return to the study site due to relocation, but moves to an area near another participating site, all efforts should be made to continue study participation at that site).
- Withdrawal of consent: subject or the subject's legally authorized representative or legally acceptable representative (LAR), as applicable in the region where the study is conducted, decides to stop participation in the study for any reason other than an AE, or is unable to complete the study as described in the study protocol. Although a subject or LAR is not obliged to give his/her reason for withdrawing prematurely, the Investigator will make a reasonable effort to obtain the reason while fully respecting the subject's rights. Every effort will be made to contact a subject or LAR who fails to attend any follow-up appointments/contacts in order to complete study assessments.
- Administrative: the Sponsor decides to terminate or discontinue the study (either at the study site or the entire study).

The reason for withdrawal will be captured on the appropriate electronic case report form (eCRF). The Study Termination form must be completed for all randomized subjects, including subjects discontinuing prior to any study drug administration. The Medical Monitor will be informed of early withdrawal of a subject from the study.

4.3.1 Subject Replacement

Subjects who do not complete the study for any reason will not be replaced.

5. STUDY MEDICATION

Study drug will only be shipped to Investigators who have provided the Sponsor (or an authorized representative) all required study documents, including Institutional Review Board (IRB)/Independent Ethics Committee (IEC) approval, have signed a final study agreement, and have been approved by the Sponsor to begin the study. Study drug will be provided by the Sponsor (or authorized representative) as blind-labeled ready-to-use bottles containing an i.v. formulation of BHR-100 or placebo ready for infusion.

5.1 Blinding and Unblinding

All site personnel will be blinded to study treatment assignment. The Investigator or designee will be responsible for drug accountability and dispensing of the study treatment infusions.

In the case of an AE or SAE for which the Investigator must know a specific treatment allocation to ensure the subject's safety, the Investigator will utilize the IWRS according to the study instructions provided. It should be stressed that unblinding the treatment allocation is only allowed for safety concerns in an emergency situation. If unblinding is required in the interest of safety and time allows, the Investigator is encouraged to discuss the matter with the study Medical Monitor whenever possible.

Whenever possible, the Investigator is to assess the relationship of the AE to the study drug before the treatment code is broken. In all cases, the Medical Monitor must be notified within 24 hours after the code has been broken.

In the case a randomization code is unblinded, a subject already undergoing study drug infusion may have the treatment discontinued at the investigator's discretion. All attempts should be made to continue all study procedures and evaluations through Month 6, unless the subject or subject's authorized representative refuses further follow-up.

5.2 Formulation, Packaging, and Labeling

BHR-100 [REDACTED]

The placebo drug product is a sterile lipid emulsion preparation of the same ingredients as BHR-100, but without the progesterone.

Both drug products are provided ready-to-use, packaged in 250 ml clear glass bottles, labeled 'For Investigational Use Only'.

5.3 Storage

All study drug must be stored in a secure limited-access area, at controlled room temperature (13 – 30° C) and protected from light, in accordance with labeled storage requirements. Room temperature must be monitored and recorded.

5.4 Dispensing

The Investigator (or designee) will dispense only the specific numbered bottles of the study treatment according to IWRS assignment.

5.5 Dosage and Administration

Subjects will be administered either BHR-100 or placebo infusion utilizing a peristaltic infusion pump. An i.v. loading dose of BHR-100 or placebo for the first hour at 0.71 mg/kg/hr will be followed by a 119-hr continuous maintenance infusion of 0.5 mg/kg/hr, for a total of 120 hours of treatment. The IWRS calculates the loading and maintenance infusion rates according to the subject's weight entered into the IWRS. The rates assigned for the subject (loading dose, followed by maintenance infusion) must be used to administer the study drug.

Study drug infusion treatment must be started within 8 hours after injury using a dedicated i.v. line (central or peripheral line).

5.6 Drug Accountability

The Investigator will maintain accurate records of the disposition of all clinical drug supplies received during the study and the dates on which drug supplies were received from the Sponsor or authorized representative.

5.7 Assessment of Compliance

Study drug will be administered by qualified clinical personnel. At the end of the study drug administration a clinical research staff member will verify that the entire dose (120 total hours from start to finish) has been administered to the subject. All details of the study drug infusion will be recorded, including any interruption and the reason. Any dose interruptions greater (>) than 30 minutes will be recorded as a protocol deviation.

5.8 Concomitant Medications

All other medications administered to or taken by the subject during the study (from time of consent through Study Day 15) are to be recorded on the eCRF. Information should be recorded for: name of drug, dose, route of administration, start and end dates and time (for i.v. drugs), and indication, including medications used for ICP management.

5.8.1 Allowed Concomitant Medications/Procedures

All medications and procedures required to treat the subject's TBI should be administered as recommended in the standard guidelines for the management of severe TBI (BTF, ABIC, and EBIC). Any therapeutic or surgical procedure performed for concurrent conditions from the time of informed consent through Study Day 15 should be recorded, including the date, description of the procedure, and clinical findings. The nature and volume of i.v. fluids will be measured on a daily basis and any other fluid/blood/blood product replacement will be documented.

5.8.2 Concomitant Medications/Therapies to be Avoided

Investigational drugs, devices, procedures or therapies should not be used at any time during the subject's 6-month participation in the study because of their potential to confound the results. Subjects participating in this clinical trial should not also be enrolled in another trial utilizing any investigational drug, device, procedure or therapy. Enrollment into a strictly observational trial is permitted, as long as the study assessments in this trial are not compromised.

6. STUDY PROCEDURES

The [Schedule of Events \(Appendix A\)](#) summarizes the frequency and timing of the required study assessments.

The subject should be managed for TBI as recommended in the BTF, ABIC, and EBIC guidelines for the management of severe TBI.

In order not to interfere with the standard of medical care and to minimize additional study-specific procedures, some of the subject's baseline characteristics will be recorded from procedures performed routinely for the management of severe TBI. Except where otherwise specified below, the last available values prior to study randomization will be recorded. These may include general (physical and neurological) examination findings. These data may even be obtained in another hospital, and are acceptable to record in the eCRF.

6.1 Screening

The following assessments will be conducted after arrival of the patient at the study hospital.

- Demographic data
- Review of inclusion/exclusion criteria
- Review of relevant medical history
- Review of medication history
- Informed Consent
- Full physical examination including:
 - Body weight
 - Right and left pupil response must be recorded
 - Injury Cause and Severity Assessment
- Vital signs
- Obtain blood samples for local lab assessments (see [Appendix B](#) for details)
- Serum or urine pregnancy test for women of child-bearing potential
- ECG
- GCS (all components: Eye opening, Verbal Response, and Motor Response)
- Baseline CT scan
- If the ICP monitor is placed, monitoring of:
 - ICP
 - TIL
- Arterial Blood Gases (ABG): While the subject is intubated, the highest value of the day for the PaCO₂ and the lowest value of the day for PaO₂, pH, HCO₃ and SaO₂, along with the accompanying Fio₂ setting, will be recorded.
- Concomitant medications/procedures

6.2 Screening and Randomization Process (IWRS)

Subjects will be randomized to either placebo or active drug on a 1:1 ratio. Randomization is stratified by region (North America, South America, Europe, and Asia). Once a subject is determined eligible for the study and informed consent has been obtained, the Investigator or designee will access the web-based randomization system (IWRS), and will reply to the system questions as prompted. All subjects (or the subject's LAR) from whom informed consent is obtained should be entered into IWRS. Screening information will be entered into the IWRS for the screened subject:

- Date and time of injury, date and time of informed consent, date of birth
- GCS
- Subject initials, gender, and weight

The IWRS will assign the Subject identification (ID) number. This assigned ID number will be used throughout the subject's participation in the study.

All screening procedures should be completed and inclusion/exclusion criteria confirmed prior to the randomization in the IWRS. Once the subject is ready to be randomized into the study, the Investigator or designee will log into IWRS, select the screened subject number and confirm inclusion/exclusion criteria. Upon confirmation, IWRS will provide a Randomization Notification including the following information:

- Assigned bottle numbers for the five day infusion;
- The loading dose infusion rate in milliliters per hour for the first hour;
- The maintenance dose infusion rate in milliliters per hour for the remaining 119 hours of administration.

Careful attention should be paid to correctly administering the assigned study drug as well as administering the assigned loading and maintenance dose infusion rates as these are calculated according to the subject's weight (see Section 5.5).

6.3 Study Drug Infusion Period: Days 1-5

The study treatment infusion MUST be initiated no later than 8 hours after the documented time of injury.

The following evaluations and assessments will be performed:

- Start and stop times of each infusion; record bottle changes
- Recording of any deviation [greater than 30 minutes] from the specified dosing times (1-hour loading dose, then 119-hour maintenance infusion) and assigned infusion rates
- Progesterone level sampling (all subjects on Day 2 (48 +/- 6 hours after initiation of the study drug infusion); additional sampling on PK subjects only)
- Daily GCS (best), if possible to assess without interfering with the subject's condition (if sedation is deemed necessary for medical reasons it should not be (temporarily) halted just to assess GCS)

- ICP, TIL for ICP management, and vital signs: The ICP, TIL and vital signs [heart rate (bpm), respiration rate (per min), systolic and diastolic blood pressure (mm Hg), temperature (C°) and pupil response] will be recorded at 00:00, 06:00, 12:00 and 18:00 hrs (+/- 30 minutes). In addition ICP, TIL and vital signs will be recorded whenever ICP management changes. If the ICP monitor is not placed, vital signs will still be collected.
- ABGs: Daily while the subject is intubated, as described in Section 6.1
- Daily fluid balance
- Neuroworsening assessment, if applicable
- Concomitant medications and procedures
- AEs
- SAEs
- Pre-injury narrative for GOS assessment: complete no later than 14 days post-randomization

6.4 Day 6: End-of-Infusion Evaluations

- GCS (best), if possible to assess (see Section 6.3)
- End-infusion CT scan (+/- 1 day scheduled at the discretion of the Investigator). It is recommended that the CT scan be completed at or near the end of the infusion; however, if the Investigator deems it necessary to obtain the CT scan on Day 5, this is acceptable.
- Full physical examination including body weight
- ICP, TIL, and vital signs, including pupil responses
- Local lab assessments (see [Appendix B](#) for details) within 1 hour after study drug infusion is completed (A pregnancy test for women of child-bearing potential is not required on Day 6)
- ABGs: While the subject is intubated, as described in Section 6.1
- ECG
- Daily fluid balance
- Concomitant medications and procedures
- Neuroworsening assessment, if applicable
- AEs (to be collected through Day 15)
- SAEs

6.5 Day 15: Post-Infusion Evaluations/Discharge

Day 15 assessments must be completed 15 days post-injury, \pm 5 days or at ICU discharge, whichever occurs earlier.

- GCS (best), if possible to assess (see Section 6.3)
- Local lab assessments (see [Appendix B](#) for details) (A pregnancy test for women of child-bearing potential is not required on Day 15)
- Concomitant medications and procedures

- Dates of ICU discharge and hospital discharge
- Neuroworsening assessment, if applicable
- AEs
- SAEs

6.6 Day 30 (Month 1) Assessments

Day 30 assessments must be completed 30 days post-injury, \pm 2 days.

- Subject status, including mortality and dates of ICU discharge and hospital discharge
- SAEs

6.7 Day 90 (Month 3) Assessments

Day 90/Month 3 assessments should be completed 90 days post-injury, \pm 14 days, during an in-person visit.

- Subject status, including dates of ICU discharge and hospital discharge
- GOS and GOS-E
- SF-36 (must be completed by the subject)
- SAEs

6.8 Day 180 (Month 6) Assessments

Day 180/Month 6 assessments should be completed at 180 days post-injury \pm 28 days, during an in-person visit.

- Subject status, including mortality and dates of ICU discharge and hospital discharge
- GOS and GOS-E
- SF-36 (must be completed by the subject)
- SAEs

6.9 Progesterone Blood Sample Collection

Blood will be collected by venipuncture on Day 2 (48 \pm 6 hours after initiation of the study drug infusion) for each subject for determination of progesterone levels by the Central Bioanalytical Laboratory.

At selected sites (10-15 US-based sites) ten (10) serial blood samples for pharmacokinetics (PK) analysis will be collected at the following times relative to the beginning of the infusion: 1, 8, 24, 48, 56, 72, 96, 104, 120, and 138 hours.

The blood samples will be taken from the arm not used for the study drug infusion. Guidelines for sample preparation, storage, packaging, and shipping will be provided to the Investigator by the Central Bioanalytical Laboratory.

7. ASSESSMENTS OF EFFICACY AND SAFETY

7.1 Efficacy Parameters

The following primary and secondary efficacy parameters will be assessed in this trial. These endpoints are described in detail in Section [7.3](#).

Primary: GOS assessment at Month 6 post- injury

Secondary (all timepoints are post-injury):

- Mortality at Month 1 and 6
- GOS at Month 3
- GOS-E at Months 3 and 6
- SF-36 at Months 3 and 6
- ICP, CPP and TIL
- Comparison of CT scans at admission and end-infusion Day 6 (+/-1 Day)

7.2 Safety Parameters

Safety and tolerability will be determined by AEs, ECGs, safety labs, vital signs, fluid balance, ABGs, and neuroworsening.

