| Interim Analysis | 
A formal interim analysis on the 6-month GOS will be performed once the first 200 subjects in each arm (400 total) have been assessed. At the planned interim analysis, a two-sided test will be conducted to detect either an increase or decrease in the common odds ratio.
 
Any consideration to prematurely discontinue the trial will be discussed by the study statistician with the DSMB and the sponsor. In order to stop the trial at an interim analysis because of favorable outcome, the significance level will need to be less than the critical p-value of 0.0003.
 |
| Safety Analysis | 
All AEs and SAEs will be summarized by counts of subjects with AEs and individual occurrences according to the MedDRA coding.
 
The following will be summarized both as the observed values and, where applicable, the changes from baseline of the values:
 
▪ Vital signs▪ Safety labs▪ ECG variables 
AE summaries will include abnormal, clinically significant lab results deemed by the Investigator as AEs.
 
Counts and percentages of subjects with each symptom of neuroworsening will be described.
 |

TABLE OF CONTENTS

| | Page |
|--|------|
| STUDY SYNOPSIS | 3 |
| LIST OF TABLES | 10 |
| LIST OF ABBREVIATIONS AND TERMS | 10 |
| 1. INTRODUCTION AND RATIONALE | 13 |
| 1.1 Background | 13 |
| 1.2 Progesterone as a Neuroprotectant: Pre–Clinical Studies | 13 |
| 1.3 Progesterone as a Neuroprotectant: Clinical Studies in TBI | 14 |
| 1.4 Rationale for Timing of Drug Administration | 15 |
| 2. STUDY OBJECTIVES | 16 |
| 2.1 Primary Objective | 16 |
| 2.2 Secondary Objectives | 16 |
| 3. STUDY DESIGN | 17 |
| 3.1 Description of Overall Study Design | 17 |
| 3.2 Study Endpoints | 17 |
| 3.2.1 Primary Endpoint | 17 |
| 3.2.2 Secondary Endpoints | 17 |
| 4. SELECTION OF STUDY POPULATION | 19 |
| 4.1 Inclusion Criteria | 19 |
| 4.2 Exclusion Criteria | 19 |
| 4.3 Withdrawal of Subjects from the Study | 20 |
| 4.3.1 Subject Replacement | 20 |
| 5. STUDY MEDICATION | 21 |
| 5.1 Blinding and Unblinding | 21 |
| 5.2 Formulation, Packaging, and Labeling | 21 |
| 5.3 Storage | 21 |
| 5.4 Dispensing | 21 |
| 5.5 Dosage and Administration | 22 |
| 5.6 Drug Accountability | 22 |
| 5.7 Assessment of Compliance | 22 |
| 5.8 Concomitant Medications | 22 |
| 5.8.1 Allowed Concomitant Medications/Procedures | 22 |
| 5.8.2 Concomitant Medications/Therapies to be Avoided | 22 |
| 6. STUDY PROCEDURES | 23 |
| 6.1 Screening | 23 |

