7.2.5 Daily Fluid Balance

The total amount of fluids administered and the total excreted once per 24 hour period will be recorded during Day 1 through Day 6.

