4.2.2 Safety

In order to determine if i.v. BHR-100 is safe and well-tolerated, the following safety variables will be summarized:

- AEs,
- Vital signs,
- Laboratory data,
- Physical examinations,
- Electrocardiogram (ECG),
- ABG, and
- Neuroworsening.

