9 STATISTICAL METHODS

All analyses and reporting of study results will be conducted using SAS V9.1.3 In addition EAST will be used to adjust for the interim analysis.

All variables will be presented using appropriate descriptive statistics according to the variable nature:

- Continuous variables: number of non-missing observations, mean, standard deviation , minimum, first quartile (Q1), median, third quartile (Q3), maximum,
- Categorical variables: number of non-missing observations, absolute and relative frequency (n and percentages (%)),
- Time-to-event variables: number of non-missing observations, number and percentage of censored observations, first quartile, median (and 95% CI), third quartile, and Kaplan-Meier survival curves.

The behavior over time of continuous variables will be analyzed by presenting descriptive statistics for each time point and the difference compared to baseline (actual values and change from baseline). The behavior over time of categorical data will be analyzed by presenting the descriptive statistics for each time point and the shift compared to baseline.

The decimal places for summary statistics and percentages will be as follows:

- Precision of data + 2 decimal places (dp) for standard deviations,
- Precision of data + 1 dp for means, medians and quartiles,
- Same precision as data for minimum and maximum,
- 1 dp for percentages except when the percentage is 100% in which case no dp would be presented, and

The primary and confirmatory efficacy analyses will be 2-sided and conducted at a 1% significance level. All secondary efficacy tests will be 2-sided and conducted at a 5% significance level.

The randomization will be stratified by region. This variable will be included as a covariate in the primary and secondary GOS efficacy analyses.

Secondary efficacy analyses will be conducted in ranked order as listed in Section 9.5.2 with the understanding that no confirmatory claims can be based on variables that have a rank lower than or equal to that variable whose null hypothesis was the first that could not be rejected at the $p<0.05$ significance level.

All exploratory analyses will be considered supportive in nature, and therefore no adjustment will be made for multiple testing of exploratory variables.

All data will be included in subject data listings for all subjects in the mITT population.

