9.6.6 Physical Examinations, ECGs, and Other Observations Related to Safety

The number and percentage of subjects with normal or abnormal physical examination findings will be presented by visit, body system (e.g. skin, HEENT, etc.) and treatment group.

Post-baseline physical examination abnormalities will be listed to provide details of the noted abnormalities.

ECGs will be performed at Day 1 prior to the initiation of study treatment and at Day 6

(post-infusion).

Abnormal rhythm, conduction, and QRS complex findings will be summarized by study day and treatment group for the safety population. Subjects with abnormal and clinically significant, abnormal post-baseline results will be listed.

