14.3.8.1 Post-baseline Abnormal ECG Results (Safety Population)

Visit ¹	Characteristic ²	Statistic	BHR-100 (N=xx)	Placebo (N=xx)
Baseline	Abnormal Rhythm	n	xx	xx
	Sinus Arrhythmia	n (%)	xx (xx.x %)	xx (xx.x %)
	Atrial Fibrillation	n (%)	xx (xx.x %)	xx (xx.x %)
	Atrial Flutter	n (%)	xx (xx.x %)	xx (xx.x %)
	Premature Ventricular Contraction	n (%)	xx (xx.x %)	xx (xx.x %)
	Other Arrhythmia	n (%)	xx (xx.x %)	xx (xx.x %)
	Abnormal Rhythm - Clin Sig	n	xx	xx
	Yes	n (%)	xx (xx.x %)	xx (xx.x %)
	No	n (%)	xx (xx.x %)	xx (xx.x %)
	Abnormal Conduction	n	xx	xx
	LBBB	n (%)	xx (xx.x %)	xx (xx.x %)
	RBBB	n (%)	xx (xx.x %)	xx (xx.x %)
	AV Block	n (%)	xx (xx.x %)	xx (xx.x %)
	QT Prolongation	n (%)	xx (xx.x %)	xx (xx.x %)
	Other	n (%)	xx (xx.x %)	xx (xx.x %)
	Abnormal Conduction - Clin Sig	n	xx	xx
	Yes	n (%)	xx (xx.x %)	xx (xx.x %)
	No	n (%)	xx (xx.x %)	xx (xx.x %)

¹ The baseline value is defined as the last measurement taken prior to first administration of study drug (Day 1).

² Clin Sig = Clinically Significant.

Program: xxxxxxx.sas, Output: xxxxxxx.rtf, Generated on: DDMONYYYY xx:xx, Page x of x

[Note to Programmer: Repeat for Baseline and Day 6.]

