BHR-100	xx-xxx	M/35/W	xx	xx-xxx	xx	xx-xxx	DDMONYYYY	(Day, 15, Day 30, Day 90, Day 180, Other) (xxxxxxxxxxxxxxxxxxxxxxxxxxxx)

¹ M = Male, F = Female, W = White, B = Black, African American or of African Heritage, P = Native Hawaiian or Other Pacific Islander, A = Asian, N = American Indian or Alaska Native, Z=Not Allowed to Obtain, O = Other.

Program: xxxxxxx.sas, Output: xxxxxxx.rtf, Generated on: DDMONYYYY xx:xx, Page x of x

Listing 16.2.4.11 Facility Transfer

Treatment Group	Subject No.	Sex/ Age/ Race ¹	Subject Discharged/Transferred From		Subject Discharged/Transferred to/Admitted To	
			Specify	Date	Specify	Date
BHR-100	xx-xxx	M/35/W	(ICU, General Ward, Nursing Home/Long-Term Care, Other ICU, Other Hospital, Rehabilitation Unit, Home, Other)	DDMONYYYY	(ICU, General Ward, Nursing Home/Long-Term Care, Other ICU, Other Hospital, Rehabilitation Unit, Home, Other) (xxxxxxxxxxxxxxxxxxxxxxxxxxxx)	DDMONYYYY

¹ M = Male, F = Female, W = White, B = Black, African American or of African Heritage, P = Native Hawaiian or Other Pacific Islander, A = Asian, N = American Indian or Alaska Native, Z=Not Allowed to Obtain, O = Other.

Program: xxxxxxx.sas, Output: xxxxxxx.rtf, Generated on: DDMONYYYY xx:xx, Page x of x

Listing 16.2.4.12 Intubation

Treatment Group	Subject No.	Sex/ Age/ Race ¹	Date/Time of Intubation	Date/Time of Extubation
BHR-100	xx-xxx	M/35/W	DDMONYYYY/ XX:XX	DDMONYYYY/ XX:XX

¹ M = Male, F = Female, W = White, B = Black, African American or of African Heritage, P = Native Hawaiian or Other Pacific Islander, A = Asian, N = American Indian or Alaska Native, Z=Not Allowed to Obtain, O = Other.

Program: xxxxxxx.sas, Output: xxxxxxx.rtf, Generated on: DDMONYYYY xx:xx, Page x of x

Listing 16.2.4.13 Daily Fluid

Treatment Group	Subject No.	Sex/ Age/ Race ¹	Visit	Collection Period Start Date/Time	Collection Period Stop Date/Time	Total Fluid Administered (ml)	Total Fluid Excreted (ml)
BHR-100	xx-xxx	M/35/W	Day 1	DDMONYYYY/ XX:XX	DDMONYYYY/ XX:XX	xxxxx.x	xxxxx.x

¹ M = Male, F = Female; W = White, B = Black, African American or of African Heritage, P = Native Hawaiian or Other Pacific Islander, A = Asian, N = American Indian or Alaska Native, Z=Not Allowed to Obtain, O = Other.

Program: xxxxxxx.sas, Output: xxxxxxx.rtf, Generated on: DDMONYYYY xx:xx, Page x of x

Listing 16.2.5.1 Study Drug Administration - Part 1

Treat- ment Group	Subject No.	Sex/ Age/ Race ¹	Dose/ Day/ Bottle/ Record	Start Date/ Time	Stop Date/ Time	Route	Infusion Rate (ml/hr)

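### Fluid balance, a named safety parameter, gets no by-arm summary in the SAP, and the ECG table omits the baseline shift that the SAP's own rule calls for

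*Protocol*

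**What the plan says.** **Fluid balance.** Protocol 7.2 Safety Parameters names seven items: "Safety and tolerability will be determined by AEs, ECGs, safety labs, vital signs, fluid balance, ABGs, and neuroworsening". Protocol 7.2.5 gives the collection rule: "The total amount of fluids administered and the total excreted once per 24 hour period will be recorded during Day 1 through Day 6". The protocol's procedures for Days 1-5 and Day 6, and its schedule of events, repeat it.

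SAP 4.2.2 introduces its safety list with the words "the following safety variables will be summarized" and names AEs, vital signs, laboratory data, physical examinations, ECG, ABG and neuroworsening. Fluid balance is not there. The data surface once, in SAP Appendices 2 and 3, as "Listing 16.2.4.13 Daily Fluid", a by-subject listing that is not marked for the DSMB.

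**ECG.** The Safety Analysis entry of the protocol synopsis covers vital signs, safety labs and ECG variables: "The following will be summarized both as the observed values and, where applicable, the changes from baseline of the values". SAP 9.6.6 says: "Abnormal rhythm, conduction, and QRS complex findings will be summarized by study day and treatment group for the safety population". The shell for Table 14.3.8.1 has a column for each arm and repeats its rows for the baseline visit and Day 6. SAP 9 sets a general rule that the behavior of categorical data over time is analyzed by presenting "the descriptive statistics for each time point and the shift compared to baseline".

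SAP 1.1, which lists changes from the protocol, mentions only the mITT population and the GOS-E method.

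**The concern.** A parameter that the protocol says will determine safety should lead to something a reader of the study report can compare between arms. For fluid balance the chain from protocol to output stops at a listing. The patients receive a 120-hour infusion while being managed for raised intracranial pressure. A difference in retained or excreted fluid is therefore a natural safety question, and these data answer it most directly.

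For ECG the gap is smaller. The table shows how many subjects in each arm were abnormal at each visit, but not how many became abnormal. A Day 6 abnormality already present at admission is counted in the same row as one that arose during the infusion.

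**Working it through.** The main check is a trace of text; no stated figure in the plan needs reproducing.

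**Step 1. Follow each of the seven Protocol 7.2 parameters into the SAP.**

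| Parameter | In SAP 4.2.2 | By-arm table | Comparison with baseline |
|---|---|---|---|
| AEs | yes | yes (14.3.1 series) | treatment-emergent by definition |
| ECG | yes | yes (14.3.8.1, Baseline and Day 6) | no shift or change |
| Safety labs | yes | yes (14.3.4 series) | change, Days 6 and 15 |
| Vital signs | yes | yes (14.3.6 series) | change |
| ABGs | yes | yes (14.3.9) | change |
| Neuroworsening | yes | yes (14.3.5) | defined as worsening |
| Fluid balance | **no** | **no** | listing only |

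One of seven has no by-arm summary; one of seven has a summary without the baseline comparison.

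**Step 2. Does the general sentence in SAP 9 on presenting all variables descriptively fill the fluid gap?** No. SAP 9.6 has no fluid-balance section, the Appendix 2 table list has no entry and Appendix 3 has no shell. A programmer working from these would produce the listing and nothing else.

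**Step 3. What the ECG table can and cannot show.** Suppose that, in one arm, n subjects have both ECGs, b are abnormal at baseline and d are abnormal at Day 6. The two counts alone leave the number newly abnormal anywhere between max(0, d − b) and min(d, n − b). If d = b, the lower limit is zero, so the table cannot distinguish no change from complete turnover. A shift table gives the number exactly. The SAP already uses this form for CT classification (Table 14.2.9). The by-subject list of post-baseline physical examination abnormalities (Table 14.3.7.2) has a Baseline column; the corresponding ECG list (Table 14.3.8.2) does not.

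**Step 4. What clinically significant ECG findings add.** Protocol 7.2.2 requires clinically significant abnormal ECGs to be recorded as AEs. Protocol 9.2 keeps pre-existing conditions out unless they worsen, and reports only the diagnosis where an ECG finding belongs to one. SAP 9.6.1 tabulates treatment-emergent events by arm. New clinically significant findings are thus already counted by arm without old ones. The missing separation concerns abnormalities judged not clinically significant.

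**Step 5. How informative a fluid table would be.** The planned infusion volume per kg is the same in both arms. The planned dose is 0.71 + 119 × 0.5 = 60.21 mg/kg, the figure in SAP 5. At the 2 mg/mL used there, 60.21 / 2 = 30.1 mL/kg. A difference between arms would not come from the planned infusion.

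The 95% CI half-width for a difference in mean daily net balance is 1.96 × SD × √(2/n per arm). The documents give no SD, so I assume 1.0 to 2.5 L.

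- All 590 per arm with data: 1.96 × 1.0 × √(2/590) = 0.11 L; with SD 2.5 L, 0.29 L.
- A deliberately harsh case for Day 6, losing as many subjects as the plan's six-month vegetative-or-dead share in the placebo assumption (29%): 0.71 × 590 ≈ 419 per arm, giving 0.14 L to 0.34 L.

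The number of patient-days is at most 1180 × 6 = 7,080; deaths and incomplete records will reduce it.

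**The case against.** The strongest reply has three parts.

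**No text promises a fluid-balance analysis.** Protocol 7.2 names it and 7.2.5 records it, but the synopsis safety assessments, the synopsis list of what will be summarized and Protocol 8.5 all omit it. This stands in part: it weakens any charge that SAP 1.1 hides a change of analysis. It does not explain how a parameter can determine safety if the arms are never compared on it.

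**Other by-arm outputs would reflect fluid retention or diuresis.** Body weight with change to Day 6 (Table 14.3.6.3), sodium, chloride and hematocrit with change, grouped electrolyte AEs, and blood pressure, ICP and CPP are all summarized. This also stands in part. Weight change is the closest, but it is a single post-baseline time point and cannot separate intake from output.

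**The ECG promise is qualified, and much of it is met.** The synopsis limits change from baseline to where it applies. In a randomized trial, the Day 6 comparison of abnormal findings in Table 14.3.8.1 (including QT prolongation) is valid without a shift. Pulse is already summarized by arm with change. The ECG listing column concerns a QT prolongation interval, so the documents do not show that an interval is recorded for every subject. All of this stands. What remains is that the shell does not carry out the rule in SAP 9.

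A reader might infer that neither assessment can show a treatment effect, or that a fluid effect would go wholly unseen. The documents do not support either reading: ECG has a by-arm table that the DSMB also receives, and fluid effects have the indirect routes just listed.

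**Conclusion.** The point holds in two parts of unequal weight. Fluid balance is a named safety parameter, collected daily for six days, and will have no by-arm summary if the SAP is followed. This is a definite gap. The ECG gap is narrow: abnormalities are tabulated by arm and visit, and new clinically significant ones are counted as AEs, but the prescribed shift is missing. New and pre-existing abnormalities that are not clinically significant therefore cannot be told apart by arm.

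The conclusion rests on the SAP text, the Appendix 2 output list and the Appendix 3 shells. It does not depend on the assumed SD. The precision range only shows that the missing table would be informative, and no document says what size of fluid difference would matter clinically. Nothing here touches the primary analysis, the error rate or the sample size.

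**What to change.** 1. Add fluid balance to SAP 4.2.2 and a short section to SAP 9.6. Add a Safety-population table of fluid administered, fluid excreted and net balance by arm for each of Days 1 to 6. Make it descriptive, with the arm difference and 95% CI, on subjects with data that day. Show the number contributing each day, because later days include only those still alive and recorded.
2. Extend Table 14.3.8.1 with a baseline-to-Day-6 shift by arm for rhythm, conduction and QRS.
3. Add a QT-interval summary with change only if the interval is recorded for all subjects. ECG heart rate is optional, because pulse already has change from baseline.

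If the sponsor prefers to keep fluid balance as a listing only, SAP 1.1 should say so and give the reason.

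The cost is one extra table, one extended table and a few more descriptive comparisons without multiplicity adjustment, which should be labeled as such. No new assessment is needed.
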